### **Prophylaxis for Bacterial Infection**

Prophylaxis for bacterial infections should be considered per institutional guidelines, especially for subjects with a history of recurrent bacterial infections or severe hypogammaglobulinemia.

### **Prophylaxis for Deep Vein Thrombosis (DVT)**

Full-dose aspirin recommended. Therapeutic anticoagulation recommended for those at high-risk of thrombosis.

### **Prophylaxis for Herpes Zoster Reactivation**

Prophylaxis for herpes zoster reactivation should be given unless contraindicated. Acceptable antiviral therapy includes acyclovir (eg, 400 mg given orally 2 times a day), famciclovir (eg, 125 mg given orally twice a day or per institutional standards), or valacyclovir (eg, 500 mg given orally, twice a day or per institutional standards), initiated within 1 week after the start of study treatment and continued at least throughout.

### **Therapy for Pneumocystis Carinii**

Pneumocystis carinii pneumonia (PCP) prophylaxis should be considered, as per institutional guidelines.

### **Prevention of Steroid-Induced Gastritis**

Dexamethasone and other steroids may induce gastritis. Medications to prevent gastritis are permitted per institutional guidelines, for example proton pump inhibitors (omeprazole or equivalent) or sucralfate, or histamine (H)2 blockers (ranitidine or equivalent).

### **Permitted Therapies**

In addition, subjects are to receive full supportive care. The following medications and supportive therapies are examples of support therapies that may be used at any time during the study:

- Antiviral medications should be considered per institutional guidelines.
- Colony stimulating factors, erythropoietin, and transfusion of platelets and RBCs. If erythropoietin is given, then this should be given according to the US prescribing information for lenalidomide and epoetin alfa, as there is an increased risk of thrombosis with lenalidomide.
- It is important to prevent constipation (eg, adequate hydration, high-fiber diet, and stool softeners if needed).
- Adequate hydration is recommended for prevention of myeloma-related kidney disease.
- Intravenous immunoglobulin (IVIG) may be considered for subjects with recurrent infection related to hypogammaglobulinemia.

- Prophylactic antiemetics, with the exception of corticosteroids
- Loperamide is recommended for the treatment of diarrhea, starting at the time of the first watery stool. The loperamide dose and regimen is according to institutional guidelines. Prophylactic loperamide is not recommended.

### **Prohibited Therapies**

Concomitant administration of any other antineoplastic therapy for the intention of treating MM is prohibited, including medications that target CD38, as well as medications used for other indications that have anti-myeloma properties (for example, interferon).

During Cycle 1, the prophylactic use of hematopoietic growth factors is prohibited.

Concomitant administration of investigational agents is prohibited. Administration of commercially available agents with activity against or under investigation for MM, including systemic corticosteroids (>10 mg prednisone per day or equivalent) (other than those given for IARs as described for Management of Infusion-Associated Reactions) should be avoided.

Nonsteroidal anti-inflammatory agents (NSAIDs) should be avoided to prevent myeloma-related kidney disease.

### **5.5 Criteria for Taking a Participant Off Protocol Therapy**

Duration of therapy will depend on individual response, evidence of disease progression and tolerance. In the absence of treatment delays due to adverse event(s), treatment may continue for until one of the following criteria applies:

- Disease progression
- Intercurrent illness that prevents further administration of treatment
- Unacceptable adverse event(s)
- Participant demonstrates an inability or unwillingness to comply with the oral medication regimen and/or documentation requirements
- Participant decides to withdraw from the protocol therapy
- General or specific changes in the participant's condition render the participant unacceptable for further treatment in the judgment of the treating investigator

Participants will be removed from the protocol therapy when any of these criteria apply. The reason for removal from protocol therapy, and the date the participant was removed, must be documented in the CRF. Alternative care options will be discussed with the participant.

When a participant is removed from protocol therapy and/or is off of the study, the relevant Off-Treatment/Off-Study information will be updated in OnCore.

## **5.6 Duration of Follow Up**

Participants will be followed every three months after removal from protocol therapy for 2 years or until confirmation of progressive disease, initiation of subsequent myeloma therapy, death, withdrawal of consent, or loss of follow up, whichever occurs first. Participants removed from protocol therapy for unacceptable adverse event(s) will be followed until resolution or stabilization of the adverse event and then every three months until PD or initiating subsequent therapy.

The first follow up visit should occur three months after the end of treatment visit.

Following disease progression or initiation of subsequent myeloma therapy, participants may be followed-up for survival by telephone contact every three months or chart review for a period of five years from study enrollment.

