**Maintenance:**

Patients must achieve a PR or better to continue onto maintenance therapy on the study.

28-day Maintenance Cycle until progressive disease (PD) or unacceptable toxicity. Subjects will be stratified based on cytogenetics (deletion (del) 17, translocation (t)(4:14), t(14;16), t(14;20), 1q duplication).

Standard-risk:

Lenalidomide 10 mg po Days 1-21

High-risk:

Carfilzomib 56 mg/m^2 (or last tolerated dose) IV Days 1, 15

Lenalidomide 10 mg po Days 1-21

Isatuximab 10 mg/kg IV Day 1 for up to 24 cycles of maintenance (two years), then discontinue

In the maintenance phase, dexamethasone, 20 mg orally or IV will be administered to subjects as a preinfusion medication prior to isatuximab dosing. When dexamethasone is reduced to 20 mg/week and is given as preinfusion medication, subjects may receive low-dose methylprednisolone ( $\leq 20$  mg) orally (or equivalent in accordance with local standards) for the prevention of delayed infusion-associated reactions (IARs), as clinically indicated.

Because lenalidomide is primarily excreted unchanged by the kidney, adjustments to the starting dose of lenalidomide are recommended to provide appropriate drug exposure in patients with renal impairment. Lenalidomide dose adjustment should be instituted for patients with a CrCl  $\leq 50$  mL/min. The recommended doses for patients with multiple myeloma and renal impairment are shown below in Table 9. If during treatment a patient's renal status changes, the dose should be adjusted as shown in Table 9. Similarly, adjustments to the starting and ongoing dosing of carfilzomib are recommended in the setting of hepatic impairment. The doses should be adjusted as shown in Table 10.

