## **5.7 Criteria for Taking a Participant Off Study**

Participants will be removed from study when any of the following criteria apply:

- Lost to follow-up
- Withdrawal of consent for data submission
- Death

The reason for taking a participant off study, and the date the participant was removed, must be documented in the CRF. In addition, the study team will ensure Off Treatment/Off Study information is updated in OnCore in accordance with DF/HCC policy REGIST-101.

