- Routine treatment or monitoring of the studied indication, not associated with any deterioration in condition, or for elective procedures of a condition unrelated to the studied indication or its treatment.
- Elective or pre-planned treatment for a pre-existing condition that did not worsen.
- Emergency outpatient treatment for an event not fulfilling the serious criteria outlined above and not resulting in inpatient admission.
- Respite care.

**Please note the distinction between seriousness and severity of an AE.** Severity is a measure of intensity of an event (mild, moderate, severe). However, the event itself may be of relatively minor medical significance; thus, a severe reaction may not necessarily be classified as a serious reaction. This differs from seriousness, which is based on patient/event outcome or action criteria described above and are usually associated with events that pose a threat to a patient's life or functioning. A severe adverse event does not necessarily need to be considered serious. **Seriousness (not severity) serves as a guide for defining regulatory reporting obligations.**

Adverse Events of Special Interest

Adverse events of special interest (AESIs): An AE of special interest (serious or non-serious) is one of scientific and medical concern specific to the sponsor's product or program, for which

ongoing monitoring and rapid communication by the investigator to the sponsor can be appropriate. Such an event might warrant further investigation in order to characterize and understand it. Depending on the nature of the event, rapid communication by the trial sponsor to other parties (eg, regulators) might also be warranted. The AEs for this study are:

- Infusion reactions:  $\geq$ Grade 3
- Infections:  $\geq$ Grade 4
- Cytopenias:  $\geq$ Grade 4
- Tumor Lysis Syndrome (if present, qualifies as Grade 3 or higher per CTCAE V5.0 guidelines)
- Intervascular Hemolysis – all grades
- New primary malignancies (if present, qualifies as Grade 3 or higher per CTCAE V 5.0 guidelines), regardless of causal relationship to study drug(s), occurring at any time for the duration of the study, from the time of signing informed consent for at least 3 years, after the last dose of investigational product.

Adverse Events of Special Interest are only reported by sites in an expedited manner if the event meets the criteria for an SAE (as per Section). All other AESIs will be collected in the SDC, but do not require immediate submission.

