Secondary Analysis: Secondary analyses will evaluate overall response rate, MRD rate, PFS and OS. Overall response rate will be percent of patients who achieve at least partial response (PR). Percent of patients achieving MR or better will also be collected as clinical benefit response. MRD rate after 4 cycles, at completion of induction, and at 24 months will be determined by deep sequencing of genomic deoxyribonucleic acid from bone marrow samples using rearranged Ig locus-specific primers (Adaptive, Seattle, WA). PFS will be defined as the time from first dose of study treatment to the first documentation of PD or death from any cause during study. OS will be defined as the time from first dose of study treatment to death from any cause. For responders, time to response (TTR) and duration of response (DOR) will be analyzed. TTR will be defined as the time from first dose of study treatment to the first documentation of response (either PR, very good partial response (VGPR) or CR, nCR, and sCR). DOR will be defined as the time from the first PR, VGPR, or CR to the first documentation of PD or death, whichever occurs earlier.

Response rates together with confidence intervals (CIs) will be provided. Kaplan-Meier curves will be used to characterize the time-to-event outcomes (PFS, OS, response duration) when there is censoring; univariate summary statistics will be provided for TTR. In addition, outcomes including median PFS and median OS will be calculated within sub-groups based on risk status (standard vs high) and MRD status (positive vs negative).

A 90% CI for the response rate will be constructed for evaluating the efficacy of KRDI. Kaplan-Meier curves will be constructed to characterize PFS, OS, and DOR. One sample standard inferences for PFS, OS, and DOR will be made accordingly.

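### Survival contact is optional, tied in section 5.6 to progression or new therapy, and absent after two years for progression-free participants who stop for reasons other than toxicity, so OS and second-cancer ascertainment are uneven

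*Combined protocol and SAP*

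**What the plan says.** Section 5.6 (Duration of Follow Up) holds three rules.

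- General rule: "Participants will be followed every three months after removal from protocol therapy for 2 years or until confirmation of progressive disease". New therapy, death, withdrawal of consent or loss to follow-up also end this follow-up, whichever comes first.
- Participants removed for an unacceptable adverse event are followed until the event resolves or stabilizes, "and then every three months until PD or initiating subsequent therapy". No 2-year limit is attached.
- Survival: "Following disease progression or initiation of subsequent myeloma therapy, participants may be followed-up for survival by telephone contact every three months or chart review", for five years from enrollment.

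Other sections bear on the same participants.

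- Section 5.2 moves a participant whose drug is held for more than 3 weeks for toxicity into a survival follow-up phase. Neither progression nor new therapy is required.
- Section 5.7 opens "Participants will be removed from study when any of the following criteria apply" and lists loss to follow-up, withdrawal of consent for data submission, and death. Completing the 2 years is not on the list.
- Section 5.1 (Maintenance) adds a way off therapy without progression: "Patients must achieve a PR or better to continue onto maintenance therapy on the study".
- Section 12.1: "OS will be defined as the time from first dose of study treatment to death from any cause".
- Section 7.1 makes new primary malignancies an event of special interest "from the time of signing informed consent for at least 3 years, after the last dose of investigational product". It separately requires second malignancies to be reported as SAEs with no time limit.
- In Tables 14A and 14B the follow-up column has no mark for AE evaluation.

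**The concern.** Whether a death is found depends on three things: whether the participant progressed, why therapy stopped, and whether the site takes up an optional contact. The first is strongly related to the risk of death, so censoring driven by it is informative, and a Kaplan-Meier OS curve assumes that it is not.

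The two main effects pull in opposite directions. Censoring progression-free participants at 2 years off therapy removes low-risk people from the later risk set and pulls OS down. Failing to contact participants after progression misses the deaths most likely to occur and pushes OS up. The balance depends on site practice, so it cannot be reliably corrected at analysis.

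OS and safety are stated secondary objectives (section 1.1.2), and section 12.1 plans median OS by risk and MRD status. The second-cancer count also needs someone to ask, and the schedule stops asking before the stated window closes.

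**Working it through.** **The plan's own figures.** The documents give no event count, precision or power for OS or second cancers. The only design calculation is for the CR rate after 4 cycles, and it reproduces by exact binomial with rates 0.27 and 0.43. With N = 50 and rejection at 19 or more, power is 0.804 and attained one-sided alpha 0.059. With N = 45 and rejection at 17 or more, power is 0.804 and alpha 0.075. Follow-up after therapy does not enter these figures.

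**Calendar check of 5.6.** Take a participant who stops at month *s* for a reason other than an unacceptable adverse event, with no progression or new therapy. Treat enrollment and first dose as the same date. Last planned contact = *s* + 24. Shortfall against five years = 60 − (*s* + 24), or zero if negative.

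| Stop month | Last contact (month) | Shortfall to month 60 |
|---|---|---|
| 6 | 30 | 30 |
| 12 | 36 | 24 |
| 24 | 48 | 12 |
| 36 | 60 | 0 |

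A participant who progresses may be contacted to month 60. One who stops for an adverse event is followed to progression or new therapy without a limit.

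**Second cancers.** The window is at least 36 months after last dose. Scheduled contact for the same participant covers at most 24, leaving 36 − 24 = 12 months or more. If progression or new therapy comes first, only the optional survival contact remains, and it ends at month 60. For a last dose after month 60 − 36 = 24, the window runs past that date.

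**Size of the OS bias (illustrative; every rate is an assumption).** Each participant moves from progression-free to progressed to dead, or dies without progression. The follow-up rules then set the censoring. Each scenario simulates 400,000 participants and compares the Kaplan-Meier estimate at 5 years with the true value.

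Model A, the 2-year limit alone with every progressor contacted: death hazard 1% per year before and 25% per year after progression; stopping without progression between about months 4 and 24.

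| Median PFS | True OS | KM, 10% stop | KM, 20% stop | KM, 40% stop |
|---|---|---|---|---|
| 4 years | 0.694 | 0.689 | 0.682 | 0.667 |
| 6 years | 0.762 | 0.757 | 0.751 | 0.737 |

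The differences run from 0.694 − 0.689 = 0.005 to 0.694 − 0.667 = 0.027, or 0.5 to 2.7 points downward.

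Model B, the limit plus incomplete contact after progression: median PFS 60 months, median post-progression survival 36 months, median time to death without progression 240 months; stopping at months 2 to 24. True 5-year OS is 0.674 (0.673 to 0.674 across runs).

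| Share stopping | All progressors contacted | 80% contacted | 50% contacted |
|---|---|---|---|
| 10% | 0.670 | 0.693 | 0.736 |
| 20% | 0.665 | 0.687 | 0.732 |
| 30% | 0.659 | 0.683 | 0.728 |

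- Limit alone: 0.674 − 0.670 = 0.004 to 0.673 − 0.659 = 0.014, about 0.5 to 1.5 points down.
- 80% contacted, net of the limit: 0.683 − 0.674 = 0.009 to 0.693 − 0.674 = 0.019, about 1 to 2 points up.
- 50% contacted, net of the limit: 0.728 − 0.674 = 0.054 to 0.736 − 0.674 = 0.062, about 5 to 6 points up. Against full contact in the same row the rise is 0.736 − 0.670 = 0.066 to 0.728 − 0.659 = 0.069, about 7 points.

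**Scale.** With N = 50 and OS near 0.69, the standard error with complete follow-up is √(0.69 × 0.31 / 50) = 0.065, or 6.5 points.

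**The case against.** The strongest reply is that the damage is limited. PFS and OS are secondary objectives, to be described in a single-arm study with no hypothesis on them. The 2-year limit alone moves OS by less than half its standard error. Participants on maintenance are assessed until progression, so the limit does not reach them. Section 5.6 already allows telephone or chart-review contact for progressors, and sites may well do it. All of this stands, and it is why the point concerns uneven ascertainment and not the validity of the trial.

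A reader might infer more than the documents support:

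- *Follow-up ends at two years for every non-progressor.* It does not. Section 5.6 follows those who stop for an adverse event with no such limit.
- *Survival contact can only open after progression or new therapy.* That is the 5.6 trigger, but section 5.2 opens a survival phase after a long toxicity hold.
- *A participant barred from maintenance for a response below PR can never become a PFS event unless they die.* Progression before new therapy is still captured by the three-monthly follow-up. Whether to follow progression through new therapy is a choice of estimand.
- *Estimated OS could read about 95%.* That figure assumes no contact with any progressor, and only restates an assumed 1% per year death rate before progression: exp(−0.05) = 0.951.
- *Late second cancers need not be reported.* Section 7.1 requires reporting whenever they occur. Follow-up visits in Table 14 also include medical history and physical examination, so the gap is in active inquiry once visits end.

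**Conclusion.** The point holds as a gap in ascertainment. As written, 5.6 leaves one identifiable group without contact after 2 years off therapy, makes survival contact optional for the group in which most deaths would be expected, and does not fit with 5.2 or 5.7. Section 5.7 keeps these participants on study but schedules nothing to fill the gap.

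The optional wording can matter more than the 2-year limit. The limit costs about 0.5 to 3 points of 5-year OS, downward. Reaching only half of progressors leaves the estimate about 5 to 6 points too high, comparable to the standard error at N = 50. These sizes rest on assumed progression, death and stopping rates, none of which is in the documents; the directions follow from the rules themselves. For second cancers, at least 12 of the 36 months can pass without scheduled contact. The CR endpoint, the sample size and its power are untouched. This is a worthwhile, inexpensive improvement and does not threaten the main result.

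**What to change.** Reconcile sections 5.2, 5.6 and 5.7 so that each route off therapy leads to one stated follow-up path. Then:

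1. State that survival *will* be recorded every three months, by telephone or chart review, until five years from enrollment for every participant, whatever the progression status or reason for stopping.
2. Ask about new malignancies at each contact until at least 3 years after last dose, and mark this in the follow-up column of Tables 14A and 14B.

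No extra disease assessments are needed, and following progression through new therapy is not part of this change.

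The cost is protocol wording plus a modest number of contacts of a kind 5.6 already uses. A participant who stops at month 6 without progression would need about 30 / 3 = 10 more survival contacts. For participants on long maintenance, some malignancy contacts would fall beyond five years from enrollment (to month 72 if the last dose is at month 36), and this should be budgeted.

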## **5.7 Criteria for Taking a Participant Off Study**

Participants will be removed from study when any of the following criteria apply:

- Lost to follow-up
- Withdrawal of consent for data submission
- Death

The reason for taking a participant off study, and the date the participant was removed, must be documented in the CRF. In addition, the study team will ensure Off Treatment/Off Study information is updated in OnCore in accordance with DF/HCC policy REGIST-101.

## **6. DOSING DELAYS/DOSE MODIFICATIONS**

Dose delays and modifications will be made as indicated in the following table(s). The descriptions and grading scales found in the revised NCI CTCAE version 5.0 will be utilized for dose delays and dose modifications. A copy of the CTCAE version 5.0 can be downloaded from the CTEP website

[http://ctep.cancer.gov/protocolDevelopment/electronic\\_applications/ctc.htm](http://ctep.cancer.gov/protocolDevelopment/electronic_applications/ctc.htm).

## 6.1 Dose and Treatment Modifications

### Isatuximab Modifications and Dose Delays

#### Dose Modification of Isatuximab

No isatuximab dose modification (increase or decrease) will be permitted.

#### Isatuximab Infusion-Associated Reactions

### General guidelines for the management of the Infusion-Associated Reactions

**Table 7 - Management of Infusion Reactions**

Symptom Severity (CTCAE ver 5.0)	Recommended Intervention
Mild (Grade 1) Infusion interruption or intervention not indicated	Continuation of isatuximab infusion per the judgement of the investigator following close direct monitoring of the patient's clinical status. Isatuximab infusion may be stopped at any time if deemed necessary. If stopped, IR will be classified as Grade 2 as per NCI-CTCAE
Moderate (Grade 2) Therapy or infusion interruption indicated but responds promptly to symptomatic treatment (eg, antihistamines, NSAIDs, narcotics, IV fluids); prophylactic medications indicated for $\leq 24$ hours	Stop isatuximab infusion. Give additional medication with IV diphenhydramine 25 mg IV (or equivalent) and/ or IV methylprednisolone 100 mg (or equivalent) as needed. Isatuximab may be resumed only after patient recovery, with slower infusion rate and with close monitoring.
Severe or life-threatening (Grade 3 or 4) Grade 3: prolonged (eg, not rapidly responsive to symptomatic medication and/or brief interruption of infusion); recurrence of symptoms following initial improvement; hospitalization indicated for clinical sequelae Grade 4: life-threatening consequences; urgent intervention indicated	Stop isatuximab infusion. Give additional medication with diphenhydramine 25 mg IV (or equivalent) and/ or IV methylprednisolone 100 mg (or equivalent) and/or epinephrine as needed. Definitive treatment discontinuation.

Patients who experience Grade 2 IAR may subsequently resume isatuximab infusion under close monitoring and supportive care as needed. Patients may receive additional premedication per the judgment of the Investigator. These patients must be informed of the potential risk of recurrent allergic reactions. The infusion must be completed within the time specified in the pharmacy manual.

